Using this strategy, we then delivered web-based information to 309 women in an academic and community clinic.⁵⁴ In this pilot, patients were randomized to receive either a web-based decision aid or a link to a standard website. Pilot participants were a median age of 59 years and 34% had less than a college degree. Most patients reviewed the websites (83%) and found this pre-consultation information highly beneficial (median score 8/10); results were similar for minority and socioeconomically disadvantaged patient subgroups.

We revised our implementation strategy in response to concerns from patients who declined pilot participation (n=68, 18% of patients approached). The most common reason was limited internet comfort or access (n=36). In response, we revised our implementation

[figure not shown]

Figure 3. Use of Internet for American Adults. Adapted from Pew Research Center surveys, 2000-2015.

strategy to include alternative ways patients could review web-based material, including emailing it to family members to review with patients and iPad access in the clinic. Several patients declined due to emotional distress (n=7) or preference to receive information directly from the surgeon (n=14). In response, we added scripts for use by clinic staff outlining the benefits of the decision aid in helping patients cope with their diagnosis, and including strong surgeon endorsement of the decision aid.

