8.3 Patients Enrolled following Institutional Crossover

The only difference between patients enrolled before institutional crossover and patients enrolled after institutional crossover is those who are enrolled after institutional crossover will have been offered the decision aid as accepted practice in the clinic. Patients will be approached for participation in the surveys and audio-recording regardless of whether or not they accepted the decision aid.

The consent process, surgical consultation, and patient surveys for these patients will be identical to those described above.

8.3.1 Decision aid: The decision aid used in this study was developed collaboratively by the Informed Medical Decisions Foundation and Health Dialog.^{35,55} Originally created as a DVD, it was converted to a web-based platform based on user feedback requesting flexibility in mode of delivery. The web-based decision aid utilizes static, didactic information written for an 8th grade reading level, and video clinical vignettes to promote consideration of personal values and preferences. It includes modules for invasive cancer, non-invasive cancer, and reconstruction. It has been used successfully in academic and community settings to increase knowledge and decrease decisional conflict.^{35,43,44,48} The greatest gains in knowledge were seen in patients with lower educational backgrounds.³⁵

8.3.2 Interviews and Focus Groups: After the clinic crosses over to the decision aid arm, clinic staff will track patients who decline the decision aid.

Patients seen in clinics that have crossed over to use of the decision aid may be eligible for participation in interviews and focus groups addressing the secondary objectives.

Patients who did not accept the decision aid:

Patients will be eligible to participate in **telephone, video, or in-person interviews** addressing Accessibility Barriers if they declined the decision aid (from clinic log). We will purposefully sample patients who experienced access barriers (identified through survey responses). If we find there is a strong association between accessibility barriers and socioeconomic disadvantage, or that accessibility barriers cluster within certain clinics, we will oversample based on those factors.

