Accessibility Barriers: We will examine barriers to accessing the web-based decision aid separately, as only patients who receive the intervention can experience these barriers. Understanding accessibility barriers is critical to ensure the intervention will not worsen disparities. This is a largely descriptive analysis that will guide sampling and interview content for the patient interviews in Aim 3. We will calculate reach of the decision aid intervention for the study cohort, and for socioeconomically disadvantaged patients. We will summarize reasons why patients declined the decision aid. We will summarize other survey responses regarding decision aid accessibility (Table 5) and perform exploratory analyses evaluating the association with socioeconomic disadvantage, using chi-square tests and odds ratios for categorical variables and ANOVA mean differences for continuous variables, respectively. Due to the exploratory nature of the analysis, sample size and power are not calculated.

Preparatory and Interactional Barriers to Patient Engagement:

Decision Aid Impact on Engagement through Mitigation of Barriers

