2. On a scale from 0 to 10, where 10 means extremely well-informed and 0 means not informed at all, how informed do you feel about surgical options for your breast cancer?

This set of questions includes some reasons other women have given for choosing their breast cancer surgery. We are interested in what is important to you. On a scale from 0 to 10, how important are each of the following to you as you consider different surgery options for your breast cancer?

How important is it to you to . . .

	Not at all important Extremely Important										
3. keep your breast?	0	1	2	3	4	5	6	7	8	9	10
4. remove your entire breast in attempt to gain peace of mind?	0	1	2	3	4	5	6	7	8	9	10
5. avoid having radiation	0	1	2	3	4	5	6	7	8	9	10

6. (*If you currently have a preference to treat your early stage breast cancer*), which treatment do you prefer?

- I am not sure
- Lumpectomy and radiation
- Lumpectomy only
- Mastectomy
- Other surgery

Other surgery: _____

7. Have you met with your oncologist to discuss treatment options prior to this visit with the surgeon?

- Yes
- No

(*If yes*), who did you meet with?

- Another surgeon
- Medical oncologist
- Radiation oncologist
- Other

(*If other*), specify _____

8. Did the clinic offer to send you a website to review before coming to see your surgeon today?

- Yes

No

If you answered "Yes" to question #8, please continue below.

If you answered "No" to question #8, please proceed directly to question #15.

9. Did you agree to have them send the website to you to review?

Yes

No

If you answered "Yes" to question #9, please continue below.

If you answered "No" to question #9, please proceed directly to question #15.

10. Were you able to review the website sent to you before coming to see your surgeon today?

Yes

No

(If yes), how much time did you spend reviewing the website that was sent to you?

Less than 15 minutes

15 - 60 minutes

More than 1 hour

(If no), why did you not review the website?

If patient is uncertain, offer categories to see if that prompts a response:

I saw my surgeon very quickly after receiving website

I didn't have internet access between when I received the website and when I saw my surgeon

I didn't receive the email

I couldn't make the link to the website work

I was feeling too stressed

I didn't think I needed any information

Other _____

11. Did you have any trouble opening or using the website?

Yes

No

(If yes), can you tell me what was hard about it?

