39. Did the information help you think about which pros and cons are most important?	1	2	3	4	5
40. Did the information help you know that the decision depends on what matters most to you?	1	2	3	4	5
41. Did the information help you organize your own thoughts about the decision?	1	2	3	4	5
42. Did the information help you think about how involved you want to be in this decision?	1	2	3	4	5
43. Did the information help you identify questions you want to ask your surgeon?	1	2	3	4	5
44. Did the information prepare you to talk to your surgeon about what matters most to you?	1	2	3	4	5
45. Did the information prepare you for a follow-up visit with your surgeon?	1	2	3	4	5

46. Where did you review the information? Check all that apply.

- On my own computer at home
- On a computer at my family or friend's home
- On my own tablet or mobile phone
- On my family or friend's tablet or mobile phone
- On a public computer (ex. library)
- On a iPad in clinic
- Other

(If other), specify _____

47. Did anyone else review the information? (Either with you or you sending them the information)

- Yes
- No

(If yes), who? Check all that apply.

- Partner/spouse
- Family member

(If family member), specify _____

- Friend
- Other

(If other), specify _____

The following questions are for all patients, regardless of whether they did and did not review any materials to help make a decision about the type of breast cancer surgery to have.

48. Would you like to receive information from the clinic?

- Yes
- No

49. What do you think would be the best format for you to receive and review information from the clinic?

- Paper version
- Computer-based version
- DVD-based version
- Other

(If other), specify _____

50. If the clinic sent web-based material prior to the first appointment with the surgeon, what would be the best way to receive this information?

- By email
- By electronic medical record, such as using a patient portal (MyChart)
- By text
- By mail
- Other

(If other), specify _____

Below are some questions so we can learn a little more about you. This information will help us understand how decision making between the surgeon and patient may be differ between patients, and how to better support patients in making their decision about breast cancer surgery.

1. What is the **highest** level of school or degree you have completed?

- Some high school or less
- High school diploma or GED
- Vocational degree or some college
- College degree

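### The only specified comparison of decision-aid access by disadvantage rests on survey items that decliners skip, so it can understate a gap that acts through declining

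*Combined protocol and SAP*

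**What the plan says.** Section 12.1.1 (Co-Primary Objective #2, Accessibility Barriers) takes accessibility separately from the preparatory and interactional barriers, "as only patients who receive the intervention can experience these barriers". It then plans three things:

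- reach, for the cohort and for disadvantaged patients;
- a summary of reasons for declining;
- a third step, in these words: "We will summarize other survey responses regarding decision aid accessibility (Table 5) and perform exploratory analyses evaluating the association with socioeconomic disadvantage".

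Only the third is a comparison by disadvantage with named methods (chi-square tests, odds ratios, ANOVA). On precision the section adds: "Due to the exploratory nature of the analysis, sample size and power are not calculated".

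In the intervention baseline survey (Appendix II), Q8 asks whether the website was offered and Q9 whether the woman agreed to be sent it. A woman who answers No at Q9 is routed past the access items by the instruction ending "to question #9, please proceed directly to question #15". She does not answer Q10 to Q14: whether she reviewed the site and why not, trouble using it, email delivery, helpfulness, and whether she would recommend it. The follow-up booklet for decliners (Appendix V) has no item on trouble with the decision aid. It does ask about wanted information, format and delivery route (Q48 to Q50), introduced by "The following questions are for all patients, regardless of whether they did and did not review any materials".

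Elsewhere, declining is itself treated as an accessibility matter. Section 10.1.4.3 lists the reason for decline under Accessibility Barriers, and Sections 5.1 and 8.3.2 make decliners eligible for the accessibility interviews. Sections 7.1.4 and 13.1.3 collect ZIP+4, from which ADI is derived, and the reason for every decliner.

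**The concern.** A woman with no usable internet may decline the website at the first telephone call. If she does, her access problem is recorded as a decline, and she contributes nothing to the items on reviewing or using the site. If such declines are commoner among disadvantaged women, the women left to answer those items are the ones whose access was good enough to accept. An association estimated in them can look flat although access differs among all women offered the aid.

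Section 12.1.1 presents this work as a safeguard against the aid widening disparities. Section 8.3.2 adds that interviews will be oversampled on disadvantage if accessibility barriers prove strongly associated with it. Under its heading for women who did not accept the aid, the same section says access barriers will be found from survey responses, although these women skip the access items. The rationale clause in Section 12.1.1 also sits badly with Section 10.1.4.3 if receiving the intervention is taken to mean receiving the aid.

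**Working it through.** **1. Who contributes to what.**

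- Q8 and Q9 (offered, agreed): all enrolled intervention-period women who reach them, decliners included.
- Q10 to Q14 (use and access): women who answered Yes at Q9 only.
- Health literacy items Q15 to Q17, and follow-up Q48 to Q50: decliners included.
- Decline log with reason and ADI: all decliners, enrolled or not (Sections 7.1.4 and 13.1.3).
- Reach: women sent the aid divided by women seen after crossover (Section 10.1.4.3), from clinic totals of offered, sent and seen (Section 7.1.4).

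ADI is available for enrolled women (Section 10.1.4.4) and for decliners. It is not collected for women who accepted the aid but did not enrol, nor for clinic patients in general. The log therefore gives a numerator by ADI without a matching clinic-wide denominator, and reach by disadvantage appears computable only among enrolled women. The plan does not say this.

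**2. Pilot figures (Section 1.5.1).** With 309 participants and 68 decliners, 68/(309 + 68) = 68/377 = 18.0%, which reproduces the stated 18%. Of the decliners, 36 cited internet comfort or access: 36/68 = 52.9% of decliners, and 36/377 = 9.5% of those approached. These women declined pilot participation, and the family-email and iPad options were added afterwards.

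**3. Illustration.** Let d be the proportion declining for an internet reason and t the proportion of accepters with access trouble. Access failure among all women offered the aid is f = d + (1 − d)t. Among accepters it is t, so d drops out of the accepter-only comparison.

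Assumptions: overall d is the pilot 9.55%; 30% of women are disadvantaged (Section 12.1.2); t is 10% in both groups. Then d(other) = (0.0955 − 0.30 × d(disadvantaged))/0.70.

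Example with d(disadvantaged) = 20%: d(other) = (0.0955 − 0.060)/0.70 = 5.1%. Failure is 0.20 + 0.80 × 0.10 = 28.0% against 0.0507 + 0.9493 × 0.10 = 14.6%. The odds ratio is (0.280/0.720)/(0.1456/0.8544) = 2.28.

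| d, disadvantaged | d, other | f, disadvantaged | f, other | OR, all offered | OR, accepters | Power, n = 282 / 332 |
|---|---|---|---|---|---|---|
| 9.5% | 9.5% | 18.6% | 18.6% | 1.00 | 1.00 | no difference |
| 12% | 8.5% | 20.8% | 17.7% | 1.23 | 1.00 | 10% / 11% |
| 15% | 7.2% | 23.5% | 16.5% | 1.56 | 1.00 | 29% / 33% |
| 20% | 5.1% | 28.0% | 14.6% | 2.28 | 1.00 | 74% / 80% |
| 25% | 2.9% | 32.5% | 12.6% | 3.33 | 1.00 | 96% / 98% |

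In the 20% row, t = 5% gives an odds ratio of 2.90 and t = 20% gives 1.78.

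Power is two-sided at 0.05 and ignores clustering. The design in Section 4.4 has 15 intervention cells of 30 data-collecting clinic-pair waves, so with equal accrual 563 × 15/30 ≈ 282 women are in the intervention period, or 332 with the 50 added after Wave 7. Treating all of them as offered the aid is a further assumption.

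**4. What reach would show.** In the 20% row, counting internet-related declines only, reach is 1 − 0.20 = 80% against 1 − 0.051 = 95%. A gap of that size should be visible if reach is computed by disadvantage among enrolled women. Reach does not separate women who declined from women never offered the aid, and does not isolate internet-related declines.

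**The case against.** A reader might infer that women without internet vanish from the accessibility assessment and that the trial could simply report no disparity. The documents do not support that. Reach among disadvantaged patients is planned, and every decline lowers it. Reasons and ZIP+4 are collected on all decliners, expressly to guard against systematic exclusion and worsening disparities. Decliners also have their own interview guide (Appendix VII). Only one component of the assessment has the gap.

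A reader might also infer that the survey comparison alone decides interview oversampling. Section 8.3.2 speaks of an association with accessibility barriers in general and names no test, and Section 13.1.3 says the decline data also inform sampling.

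Three further objections have force:

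- The rationale clause can mean intervention-period as opposed to usual-care patients, which would make it loose wording and not an exclusion of decliners.
- Table 5, which would list the tested items, is not in the document, and decliners do answer Q8, Q9, the literacy items and Q48 to Q50. Conditioning on acceptance is established only for Q10 to Q14, and those skips are unavoidable: a woman never sent the site cannot report trouble opening it.
- The decline rates by disadvantage are invented, and setting t equal in both groups forces the accepter-only odds ratio to 1.00.

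All of this limits the point. What remains is that no comparison of declining by disadvantage is stated, and that reach as defined lacks ADI in its denominator and so does not fully fill the gap.

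**Conclusion.** The point holds in a limited form. For Q10 to Q14, the specified association with disadvantage is conditional on acceptance and carries no information about a disparity that acts through declining. The planned reach, decline summary and interviews reduce the consequence, but none of them is specified as a comparison of declining, or of internet-related declining, by disadvantage.

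The size of any bias cannot be determined from the documents. Under the stated assumptions the odds ratio among all women offered the aid lies between 1.00 and 3.33, and modest gaps would be detected with low power even after the change. The pilot 9.5% is only a guide to how common such declines may be. The analysis is exploratory, so no primary endpoint, error rate or sample size changes. The change is still worth making, because the plan relies on this analysis to check that the aid does not worsen disparities.

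**What to change.** In Section 12.1.1:

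- State that all intervention-period women offered the aid can experience accessibility barriers.
- Among enrolled women offered the aid (Q8 Yes), add two outcomes to the exploratory comparisons by ADI:
  - (a) declined (Q9 No);
  - (b) access-related failure: declined for an internet or access reason in the log; or accepted but had trouble using the site (Q11); or accepted but did not review it for an access reason at Q10 (no internet, email not received, link not working). Non-review because of stress or no perceived need does not count. Classify the remaining Q10 answers before analysis.
- State that reach by disadvantage uses this enrolled denominator.
- Report logged decline reasons by ADI for all decliners, so that women who decline both the aid and the research are still described.
- Label the accepter-only survey results as conditional on acceptance.

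In Section 8.3.2, let the oversampling rule consider (a), (b) and the decline log together.

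Cost: wording and two added comparisons. Q8, Q9, ADI and decline reasons are already collected. The one practical burden is that the decline list is submitted de-identified (Section 6.1), so site staff must link the logged reason to the study record for enrolled decliners. They hold the medical record number needed to do this.

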12.1 Analysis Plan for Co-Primary Objectives

12.1.1 Primary Analysis

Co-Primary Objective #1: The goal is to evaluate the effectiveness of a decision aid in increasing patient engagement in decision making in clinics serving a high proportion of socioeconomically disadvantaged patients. We will follow an intention to treat approach, using all available data, regardless of group assignment or whether patients viewed the decision aid. The data as collected will have a nested structure: patients nested within surgeons within surgical clinics, this last level being the formal level of intervention. Descriptive analyses will summarize patient, surgeon, and clinic characteristics. When reporting these summary data, we will report as “NR-Not reported” any cell where the number of patients is less than five to avoid inadvertent patient identification. We will test intervention effects in the framework of generalized linear mixed effects models with an “intervention versus usual care” dummy variable (which varies over patients within each surgeon and clinic), a surgeon random effect, and a clinic random effect. Analysis models will include two additional parameters, for wave and wave-squared, respectively to flexibly control for potential time effects and to allow for a non-linear relationship with outcome measures. We will include a post-COVID restart dichotomous variable that reflects whether a patient is enrolled during the post-COVID restart time period for a given site (yes/no). We also will include time (in units of wave) post-COVID in all models. These indicator and time parameters allow for the control of sites restarting the trial post-COVID shut down at different times. This leads to the following planned linear mixed effects model for the two primary outcomes (y) in Aim 1, namely, PEPPi-5 self-efficacy and Active Patient Participation Behaviors:

$$y_{ijk} = \beta_0 + \theta x_{ijk} + \beta_1 t_{1ijk} + \beta_2 t_{1ijk}^2 + \beta_3 z_{ijk} + \beta_4 t_{2ijk} + u_k + u_{j(k)} + e_{i(j(k))}$$

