We will first perform analyses to test and quantify the extent to which the effect of the decision aid intervention on patient engagement endpoints is mediated through the mitigation of candidate preparatory and interactional barriers. We will quantify the indirect effect relative to the total effect of the decision aid in joint linear structural equation models (SEM) for the endpoint and the candidate mediators, including random surgeon effects and random region effects for each of the mediator and endpoint parts of the models. Each of the preparatory and interactional Barriers will be represented by a continuous latent construct in the SEM, with 3 and 5 observed items for Preparatory and Interactional Barriers, respectively. Binary or count variables will be modeled via latent continuous construct in the SEM. Structural equation models will be specified, estimated and tested using Mplus v7.3.⁹⁷ The use of unidimensional latent constructs increases power and reduces the number of tests, relative to testing each observed item separately. Standardized coefficient estimates from the SEM, representing total, direct, and indirect effects, will allow for the determination of whether the mechanism by which the decision aid leads to increased patient engagement is through the mitigation of preparatory and/or interactional barriers (see Figure 7 for simplified example). For example, if coefficient X is important but Y is not, we can conclude that although the decision aid leads to statistically significant changes in interactional barriers, this is not the mechanism through which the decision aid increases patient engagement. Alternatively, if only coefficient Y is important, we can conclude that although the interactional factors represent a significant barrier to patient engagement, the decision aid does not significantly impact the barrier.

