Finally, if we find significant indirect effects (represented in the figure by the dashed line leading from the decision aid to engagement that runs through interactional barriers), we can conclude that receipt of the decision aid leads to a change in the interactional barrier, which leads to improved patient engagement. Statistically, coefficients X and Y will be tested together, with the null hypothesis being that the product $XY=0$. If either latent construct for preparatory or interactional Barriers is significant, then each individual observed item will be tested, post hoc, as candidate barriers. Candidate barriers for the next models will be barriers for which the indirect effect is significant and/or barriers associated with lower levels of engagement (i.e. coefficient Y). Those barriers associated with lower level of engagement will be considered persistent and prioritized for inclusion in the qualitative interviews (Aim 3).

Persistent Barriers Experienced by Socioeconomically Disadvantaged Patients

We will estimate logistic and Poisson regression models with socioeconomic deprivation as the explanatory variable, and each candidate persistent barrier as described above as the outcomes, in order to assess the extent to which socioeconomic disadvantage is associated with persistent barriers to engagement. As with Aim 1, models will include surgeon and clinic random effects to account for patient clustering. Findings will guide the sampling strategy for patient interviews (Aim 3) and will be incorporated into the interview content.

[figure not shown]

Figure 7. Schematic depicting the mediating role of preparatory and interactional barriers on engagement. The dashed lines represent the test for the overall effect of whether the decision aid improves engagement through that pathway.

*Effect of decision aid on barriers; +Effect of barriers on patient engagement.

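### The exploratory accessibility-by-disadvantage tests ignore clustering by clinic and surgeon, although the Aim 1 models and the parallel persistent-barrier models allow for it

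*Combined protocol and SAP*

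**What the plan says.** In the combined protocol and SAP, Section 12.1.1 (Accessibility Barriers) relates survey responses about access to the decision aid to disadvantage "using chi-square tests and odds ratios for categorical variables and ANOVA mean differences for continuous variables, respectively". No clustering term is named. The status claimed is modest: "This is a largely descriptive analysis that will guide sampling and interview content for the patient interviews in Aim 3", and "Due to the exploratory nature of the analysis, sample size and power are not calculated".

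The rest of Section 12.1.1 treats the data as clustered:

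- The structure is described as "patients nested within surgeons within surgical clinics, this last level being the formal level of intervention".
- The Aim 1 model has "a surgeon random effect, and a clinic random effect".
- For persistent barriers regressed on disadvantage, "models will include surgeon and clinic random effects to account for patient clustering".
- The mediation structural equation model is specified differently, "including random surgeon effects and random region effects for each of the mediator and endpoint parts of the models".

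Section 8.3.2 says what follows from the accessibility results. If barriers are strongly associated with disadvantage, "or that accessibility barriers cluster within certain clinics, we will oversample based on those factors". Section 12.1.2, in the power calculation for persistent barriers, assumes that 30% of the sample is disadvantaged and that these women are spread evenly over clinics and surgeons.

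**The concern.** The accessibility analysis and the persistent-barrier analysis have the same explanatory variable and the same use, which is to steer interview sampling and content. One allows for clustering and the other does not, and no reason is given.

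Clustering is plausible on both sides. Each clinic's own staff offer and send the aid (Section 7.1.2), under an implementation worked out clinic by clinic (Section 7.1.3). Disadvantage is a property of the neighbourhood (Section 10.1.3), and the sites are geographically dispersed and stratified mainly by minority/underserved status (Section 4.7.1).

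If both variables do vary between clinics, two things follow. Women in one clinic are counted as independent, so standard errors are too small. And an association created by how one or two clinics deliver the aid looks the same as one arising between women within a clinic. The opposite arrangement could hide a real disparity. Section 8.3.2 lists association with disadvantage and clustering by clinic as separate reasons to oversample, and the planned tests cannot tell them apart. Section 12.1.1 itself values splitting the variance by surgeon and clinic, because it shows the level at which an added intervention might work.

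**Working it through.** **The plan's nearest figure.** No power or error figure is given for the accessibility tests. The closest is the persistent-barrier-by-disadvantage test in Section 12.1.2: N = 563, 30% disadvantaged, two-sided alpha 0.0125. The detectable standardised difference is (z for 1 − alpha/2 + z for power) / √(N × 0.3 × 0.7).

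- N = 563: 0.307 at 80% power and 0.348 at 90% (stated: 0.31 and 0.35).
- N = 613, with 50 more patients: 0.294 and 0.333 (stated: 0.30 and 0.34).

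The plan's figures reproduce with no design effect, which is consistent with its assumption that disadvantage is spread evenly.

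**Exposed women.** In the Section 4.4 schedule, two clinics cross over at each of waves 2 to 6, and the crossover wave is not used for data. For each pair of clinics, intervention waves number 5, 4, 3, 2 and 1 (15 in all) and usual-care waves 1, 2, 3, 4 and 5 (also 15). With equal accrual per clinic-wave (an assumption), half of 563 is about 282, or m = 28.2 per clinic. Adding the 50 extension patients gives about 332.

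**Effect of ignoring clinic.** For a crude comparison in which exposure and outcome both cluster, the design effect is DE = 1 + (m − 1) × ICC(disadvantage) × ICC(barrier). The actual error of a nominal 5% test is 2 × [1 − Φ(1.96/√DE)]. The documents give neither ICC. I borrow 0.07 for the barrier from the PEPPI-5 assumption in Section 12.1.2 and vary the other. Example at 0.1: DE = 1 + 27.2 × 0.1 × 0.07 = 1.190, so the error is 7.2%. The simulation column is an unadjusted Pearson chi-square with 10 clinics of 28, 30% disadvantaged, an assumed 20% barrier rate and 20,000 runs.

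| ICC of disadvantage | DE | Type I error, formula | Type I error, simulation |
|---|---|---|---|
| 0 (even spread) | 1.000 | 5.0% | 5.2% |
| 0.1 | 1.190 | 7.2% | 7.1% |
| 0.2 | 1.381 | 9.5% | 9.2% |
| 0.3 | 1.571 | 11.8% | 11.3% |

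The true standard error is √DE times the naive one: 1.09 times at 0.1 and 1.25 times at 0.3.

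**Sensitivity.**

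- Barrier ICC 0.01: at most 6.0%.
- Barrier ICC 0.14 with disadvantage ICC 0.3: 18.1% by formula, 16.6% by simulation.
- 332 women, barrier ICC 0.07: 5.0% to 13.0% over disadvantage ICCs of 0 to 0.3.
- A different simulation model (331 women, 25% barrier rate, ICCs on the latent scale of 0.05–0.10 for the barrier and 0.05–0.20 for disadvantage) gave 5.1% to 7.9%. The size therefore depends on modelling choices.

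**Confounding by clinic, with assumed values.** Let three of ten equal clinics have 50% disadvantaged and 40% with a barrier, and the other seven 21.4% and 18.6%, with no association inside any clinic. Overall rates are 30% and 25%. The joint proportion is 0.3 × 0.50 × 0.40 + 0.7 × 0.214 × 0.186 = 0.088. The other cells are 0.212 (disadvantaged, no barrier), 0.162 (barrier, not disadvantaged) and 0.538 (neither). The pooled odds ratio is (0.088 × 0.538)/(0.212 × 0.162), or 1.37 with unrounded cells, although it is 1 within every clinic.

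**The case against.** Much of the case on the other side stands.

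- **Status.** The analysis is labelled exploratory, carries no alpha or multiplicity rule, and feeds purposeful sampling for 30 interviews (Section 12.2.3). Strict error control is not needed there.
- **Trigger.** Section 8.3.2 acts on a strong association, not on p < 0.05, so the rejection rates above do not describe the plan's decision rule. They only show how far the standard errors may be off.
- **Premise.** No document shows that disadvantage differs between the clinics. Section 12.1.2 assumes an even spread, and under that assumption there is no inflation. Section 8.3.2 provides for clinic clustering of barriers as a possibility and does not predict it.
- **Numbers.** In Appendix II, women who were not offered the website or declined it skip questions on its use. Fewer respondents per clinic means less inflation.
- **Estimand.** If disadvantaged women have poorer access because they attend clinics that deliver the aid poorly, that is a real disparity. The crude odds ratio captures it, and a purely within-clinic one would remove it.
- **Sparse data.** On the assumed rates, 282 × 0.30 × 0.20 is about 17 disadvantaged women with a given barrier, over 23 surgeons. A logistic model with two random effects would be thinly supported.

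A reader might also infer that the accessibility tests are the only patient-level analysis without clinic and surgeon effects. The text does not support that: the mediation model names surgeon and region effects and does not mention clinic.

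These points limit the size and shape the remedy. They do not explain why two parallel analyses of disadvantage are handled differently, and they leave the crude tests unable to separate the two grounds for oversampling.

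**Conclusion.** The concern holds as a minor point. The planned accessibility tests take no account of clinic or surgeon, while the Aim 1 and persistent-barrier models do. If disadvantage is evenly spread, nothing is lost on error rate. If it varies between clinics with an ICC of 0.1 to 0.3 and the barrier ICC is 0.07, a nominal 5% test runs at about 7% to 12%. This rests on about 282 exposed women in ten equal clinics, and on ICCs and a barrier rate that are assumptions. Surgeon clustering was not modelled separately.

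A stronger reading would be that a false disparity finding is likely, or that a confirmatory result of the trial is at risk. The documents support neither: between-clinic variation in disadvantage is not shown, and no confirmatory test uses these results. What is at stake is the interpretation of an accessibility disparity and the choice of whom to interview.

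**What to change.** In Section 12.1.1, Accessibility Barriers:

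1. Keep the crude odds ratios and mean differences as the description of overall disparity, but base their confidence intervals and tests on methods that account for clinic. With only ten clinics, a robust variance would need a small-sample correction.
2. Add a clinic-adjusted estimate for each item: a logistic or linear mixed model with clinic and surgeon effects, as already planned for persistent barriers. Where items are sparse, use a clinic-stratified Mantel-Haenszel odds ratio or clinic fixed effects. The last two isolate the within-clinic association. A plain random-intercept model does so only if the clinic mean of disadvantage is entered separately.
3. Report both estimates side by side, labelled exploratory, so that the two oversampling grounds in Section 8.3.2 can be judged separately.

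The cost is a sentence or two of SAP wording, slightly more analysis work and somewhat wider intervals. No new data are needed.
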